3.2 Study Design

This safety and tolerability study of intravenous (IV) SAB-176 consists of up to 4 single dose-levels or cohorts (cohort 1–4) in a double-blind, randomized, placebo-controlled dose-escalating cohort design. Four cohorts of 2–10 subjects each will be administered a single IV dose of SAB-176 or saline placebo. At very low doses, the concern is primarily allergic or T-cell activation/cytokine storm, so small cohort sizes should be utilized. As the target dose is approached, the sample size will increase to increase the likelihood of detecting toxicity events. The cohorts and dose levels are outlined in [Table 1](#).

Table 1: Cohorts and Dose Levels

Cohort	Number of Subjects Receiving SAB-176				Number of Subjects Receiving Saline Control
	1 mg/kg	10 mg/kg	25 mg/kg	50 mg/kg	
1	2				1
2		4			2
3			6		2
4				8	2

The number of subjects dosed will follow the limitations below:

- The first three subjects of each cohort will be dosed every other day (48-hour interval).
- For Cohorts 2–4, 48 hours after the third subject is dosed, up to 3 subjects may be dosed per day, until the cohort is completed, and no more than 8 subjects will be dosed per week.
- For cohorts 2, 3, and 4, additional dosing in the cohort may continue only after the safety committee recommends continuation after reviewing the safety data from the 3 initial subjects of the cohort.
- After the first three in each cohort, subsequent subjects will be observed for at least 4 hours before beginning the next infusion in the next subject.

Table 2. Example of dosing timeline

	Infusion Day								
	1	2	3	4	5	6	7	8	9
Subject 1	X								
Subject 2			X						
Subject 3					X				
Subject 4							X*		

Table 2. Example of dosing timeline (con't)

	Infusion Day								
	1	2	3	4	5	6	7	8	9
Subject 5							X (≥4 hrs post Subject 4)		
Subject 6							X (≥4 hrs post Subject 5)		
Subject 7								X	
Subject 8								X (≥4 hrs post Subject 7)	
Subject 9								X (≥4 hrs post Subject 8)	
Subject 10									X

* Additional enrollment in the cohort may continue only after the safety committee recommends continuation after reviewing the safety data from the three initial subjects of the cohort.

NOTE: Only 1 subject should be infused at any given time. An infused subject should be observed for at least four hours prior to beginning the next infusion.

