5.3 Dosing and Administration

The NIH clinical center guidelines for administration of a standard human 10% IVIg (10g/100mL) are for the initial rate to be 0.6 mL/kg/hr, and the rate can be increased gradually to a maximum of 4.8 mL/kg/hr, if tolerated.

SAB-176 will be prepared in the following dilutions:

- Cohort 1 will be prepared as a solution 1mg/1ml (0.1% solution by weight), which is 1/100th the concentration of standard human IVIg (e.g. Gammunex).
- Cohort 2 will be prepared as a solution 4mg/1ml (0.4% solution by weight), which is 1/25th the concentration of standard human IVIg.
- Cohorts 3&4 will be prepared as a solution 20mg/1ml (2% solution by weight), which is 1/5th the concentration of standard human IVIg.

The dose of study drug will be calculated based on the subject's dose cohort and weight (up to a maximum weight of 100 kg). The pharmacy will prepare a bag containing the dose of SAB-176 plus as much normal (0.9%) saline as is needed to reach the above listed concentrations. The infusion will be provided in an opaque bag to obscure the bag (as the SAB-176 may develop

bubbles like IVIg if agitated). The drip chamber will also be covered, but accessible if needed by nursing staff for verification of flow rate, etc.

Table 3: Dosing and Administration

Cohort	Dose (mg/kg)	Concentration	Start Rate (mL/kg/hr)	End Rate (mL/kg/hr)	Start Rate (mg/kg/hr)	End Rate (mg/kg/hr)	Proportion of Human IVIG Rate	Duration (mins) (approx.)
1	1	1 mg/mL (0.1%)	0.5	2	0.5	2	1/120 th – 1/240 th	53
2	10	4 mg/mL (0.4 %)	0.5	3	2	12	1/30 th - 1/40 th	85
3	25	20 mg/mL (2 %)	0.5	1	10	20	1/6 th - 1/12 th	83
4	50	20 mg/mL (2 %)	0.5	2	10	40	1/6 th - 1/10 th	97

The infusion will be started at of 0.5 mL/kg/hr, escalating by 0.5 mL/kg/hr increments every 15 minutes to a maximum specified above (end rate).

It is anticipated that the infusion is prepared the morning of the infusion. Since the study drug has been shown stable for 24 hours when mixed in saline, the infusion should be started within 6 hours of preparation in order to assure completion within normal working hours.

The dosing of an individual subject will be slowed and or stopped (depending on clinical assessment) for the following:

- hypotension (systolic or mean blood pressure decreases by 20 mmHg)
- shortness of breath, wheezing, or desaturation
- pain, tenderness, erythema, or swelling around the infusion site
- fevers, chills

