11.7 Pausing Rules

If any of the following criteria are met at any time the study will be paused to further enrollment until assessed by the sponsor medical monitor:

- Any SAE as defined in Section 10.3 that can be possibly, probably, or definitively attributed to the study drug
- Three or more subjects in the same cohort experiencing the same Grade 2 or higher adverse effect that can be possibly, probably, or definitively attributed to the study drug
- Two or more subjects develop the same or clinically similar Grade 3 AE or laboratory abnormality
- Two or more subjects develop a serum creatinine \geq Grade 2 toxicity (≥ 1.8 mg/dL)
- Two or more subjects develop \geq 1.5-fold increase in serum creatinine level from baseline
- Two or more subjects develop GFR <70 mL/min, irrespective if serum creatinine is normal range or Grade 1
- Two or more subjects develop a serum creatinine \geq Grade 2 toxicity in PT and/or PTT (i.e. one grade 2 PT and one grade 2 PTT would meet this pausing rule)

The sponsor medical monitor can request information needed (such as a listing of graded AEs) and unblinded randomization scheme (directly from the site investigational pharmacy group) to evaluate the data. For individual subject unblinding, the site will follow their unblinding procedures per SOP-AUSCLN-506. The sponsor medical monitor will ultimately make the decision to either resume the study or stop the study.

If the trial is stopped due to unacceptable adverse events or stopping criteria, the IRB will be notified.

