11.8 Dose Escalation Rules

When the results from the Day 7 visit for the last subject in a cohort (e.g., Cohort 1) are available safety parameters will be analyzed to determine the overall safety of that dose-level (e.g., 1 mg/kg). If any of the following criteria are met, the corresponding dose-level is not considered “acceptably safe”, and the study will not proceed to the next higher dose group (as the review is blinded, this will be across treatment arms).

- Any SAE that can be possibly, probably, or definitively attributed to the study drug
- Any immediate hypersensitivity or cytokine storm events
- Two or more subjects with asymptomatic positive anti-IgG (rheumatoid factor)
- One or more subjects with positive anti-IgG (rheumatoid factor) with associated rheumatologic symptoms (i.e. arthralgia, myalgia, etc.)
- Two or more subjects across all cohorts experience the same Grade 3 or higher adverse effect that can be possibly, probably, or definitively attributed to the study drug

- Three of the first 10 subjects (30%) experience the same grade 2 or higher adverse effect that can be possibly, probably, or definitively attributed to the study drug or any time thereafter 30% of enrolled subjects have the same grade 2 or higher 'related' AE.
- Two or more subjects across cohorts develop a serum creatinine \geq Grade 2 toxicity (≥ 1.8 mg/dL) or doubled from baseline (whichever is lower)

If any of the above criteria are met at any time, then the medical monitor will evaluate unblinded study data and make a determination about continuation of the study and/or amendment of the protocol.

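### In Cohort 1 the two SAB-176 recipients alone cannot meet the Grade 2 pausing criterion, so a general Grade 2 reaction in both requires no pause or unblinded review before 10 mg/kg

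*Protocol*

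**What the plan says.** Table 1 in Protocol 3.2, under "Number of Subjects Receiving SAB-176", assigns 2, 4, 6 and 8 subjects to 1, 10, 25 and 50 mg/kg, with 1, 2, 2 and 2 saline controls.

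Under 11.7, if a criterion is met, "the study will be paused to further enrollment until assessed by the sponsor medical monitor". The Grade 2 criterion is "Three or more subjects in the same cohort experiencing the same Grade 2 or higher adverse effect", limited to events at least possibly attributed to study drug. The monitor may ask for the unblinded randomization scheme but is not required to.

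Section 11.8 governs escalation. It reviews each cohort after the last subject's Day 7 visit, blinded and pooled over arms. Its general Grade 2 criterion is "Three of the first 10 subjects (30%) experience the same grade 2 or higher adverse effect", again related, and after that a 30% share of enrolled subjects. If an 11.8 criterion is met at any time, the monitor must evaluate unblinded data.

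For Cohorts 2 to 4, section 3.2 adds that "additional dosing in the cohort may continue only after the safety committee recommends continuation after reviewing the safety data from the 3 initial subjects". It also explains the small early cohorts: "At very low doses, the concern is primarily allergic or T-cell activation/cytokine storm".

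**The concern.** The count of three is fixed while cohort size is not. As a share of SAB-176 recipients it is 3/2 = 150% in Cohort 1, then 3/4 = 75%, 3/6 = 50% and 3/8 = 37.5%. Only in Cohort 1 is it out of reach for the recipients alone.

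There it can fire only when the saline subject is affected too, which is when attribution to drug is weakest. The most drug-specific pattern, with both recipients affected and saline clear, cannot trigger it. This happens just before the tenfold step from 1 to 10 mg/kg, the largest relative step in the trial.

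The relevant events are ordinary ones. Section 8.1.1 lists headache, nausea, fatigue, pyrexia and site reactions as common with human IVIg. At stake is whether such a pair must be assessed by the medical monitor, with the allocation known, before anyone receives 10 mg/kg.

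**Working it through.** **1. The plan's own figures.** SAB-176: 2+4+6+8 = 20. Saline: 1+2+2+2 = 7. Total 27, as stated. Three of 10 is 30%, as stated. Cumulative size after each cohort is 3, 9, 17 and 27, so the first 10 subjects are all of Cohorts 1 and 2 plus the first subject of Cohort 3.

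**2. Each criterion against the case.** The case is the same related, non-serious Grade 2 event in both Cohort 1 recipients, with saline clear.

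| Criterion | Needs | Result |
|---|---|---|
| 11.7 and 11.8, related SAE | 1 | Not met: non-serious |
| 11.7, Grade 2 | 3 in one cohort | Not met: 2 |
| 11.7 and 11.8, Grade 3 | 2 | Not met: Grade 2 |
| 11.7 creatinine, GFR, PT/PTT; 11.8 creatinine | 2 | Catches those events only |
| 11.8, immediate hypersensitivity or cytokine storm | 1 | Catches those events only |
| 11.8, rheumatoid factor | 2 without symptoms, 1 with | Catches those findings only |
| 11.8, general Grade 2 | 3 of first 10 | Not met: 2 of 10 = 20% |
| 11.8, 30% clause | after the first 10 | Not yet in force |

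The gap is therefore confined to Grade 2 events outside the organ-specific and immune criteria.

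**3. Chance that the 11.7 criterion fires in Cohort 1.** The protocol gives no event rates, so these are assumptions. Let p be the chance of the event, judged related, in each recipient and q the chance in the saline subject.

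- Current count of three: p²q. Given that both recipients are affected, it fires with probability q.
- Count of two: p² + 2p(1−p)q.

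| p (with q = 0) | 0.09 | 0.25 | 0.50 | 0.75 | 1.00 |
|---|---|---|---|---|---|
| Count of three | 0 | 0 | 0 | 0 | 0 |
| Count of two | 0.008 | 0.06 | 0.25 | 0.56 | 1.00 |

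**4. When 11.8 catches the pair.** Given 2 of 2 and q = 0, one more match among Cohort 2's four recipients completes three of the first 10. With 4 SAB-176 and 2 saline subjects in random order, the first three dosed include 1, 2 or 3 recipients with probability 4/20, 12/20 and 4/20.

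- Within the first three: 1 − [0.2(1−p) + 0.6(1−p)² + 0.2(1−p)³]
- Within Cohort 2: 1 − (1−p)⁴
- Expected recipients dosed at 10 mg/kg when the criterion is met, or four if it is not met in Cohort 2: [1 − (1−p)⁴]/p, assuming each outcome is known before the next SAB-176 dose

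| p | 0.25 | 0.50 | 0.75 | 1.00 |
|---|---|---|---|---|
| Within the first three | 0.43 | 0.725 | 0.91 | 1.00 |
| Within Cohort 2 | 0.68 | 0.94 | 0.996 | 1.00 |
| Recipients dosed by then | 2.7 | 1.9 | 1.3 | 1.0 |

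If Cohort 2 has no match, subject 10 can still complete the count.

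**5. Unneeded reviews with a count of two.** Suppose there is no drug effect and all three subjects have a 9% rate. That figure is borrowed from 8.1.1, where it is all-grade headache for a different product. Count of two: 3 × 0.09² × 0.91 + 0.09³ = 0.023. Count of three: 0.09³ = 0.0007.

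**The case against.** The strongest reply is that this is a choice of calibration and that little slips through.

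- The counts rise as severity falls: one related SAE, two Grade 3, three Grade 2. The low-dose concern named in 3.2 is allergic and cytokine events, and 11.8 acts on one of those.
- By the time both recipients are affected, Cohort 1 is complete or only the saline subject remains. Escalation already waits for Day 7 results and an assessment of overall safety, and a core committee of at least four members must authorize advancement (11.4).
- The investigator may interrupt enrollment for adverse events (11.2.1), and under 5.3 "The dosing of an individual subject will be slowed and or stopped" for fever, chills or site reactions.
- In Cohort 2 the first three subjects are dosed 48 hours apart, with a committee check before the fourth.

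Most of this stands, and it is why the consequence is small. None of it, however, requires a pause or an unblinded look for this pattern. The Day 7 review sees 2 of 3 affected without the split, and section 5.3 protects the individual subject rather than prompting study-level review.

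A second reply is that changing the count in 11.7 would not by itself secure an unblinded look, because 11.7 leaves unblinding optional. That is correct, and the fix has to say so explicitly.

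A third is that high event rates at 1 mg/kg have no support in the protocol, which reports that a related product from the same platform was well tolerated at 50 mg/kg. That also stands. At p = 0.09 the pair has probability 0.008, and a related Grade 2 rate would probably be below an all-grade one.

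**Conclusion.** The point holds within limits. In Cohort 1 the SAB-176 recipients alone cannot meet the 11.7 Grade 2 criterion, whatever the event rate. For a related, non-serious Grade 2 event outside the specific criteria, with saline clear, nothing in 11.7 or 11.8 is met before 10 mg/kg dosing begins. The consequence is minor: mainly a later mandatory look.

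A reader might infer three stronger things that the protocol does not support.

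- **That the pair is lost.** It is not. The 11.8 count runs across cohorts and applies at any time, so one more match in Cohort 2 or in subject 10 brings mandatory unblinded review.
- **That 2.7, 1.9 or 1.3 recipients would be spared exposure.** Those figures say when a written criterion is met, given 2 of 2 and an assumed p, and the monitor may resume after a pause. Weighted by the chance of the pair, 2.7 becomes 0.0625 × 2.73 = 0.17 at p = 0.25.
- **That no safety document covers the case.** The check reaches 11.7 and 11.8 only. The Safety Review and Communications Plan and the Safety Monitoring Plan are not shown and may hold further triggers.

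The count itself needs no assumption. The probabilities rest on assumed p and q, and those in step 4 also on equal p at 1 and 10 mg/kg.

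**What to change.** Reword the 11.7 Grade 2 criterion to require two or more subjects in Cohort 1, or three or more within any one of Cohorts 2 to 4, keeping the relatedness condition. Add a sentence: when the Cohort 1 criterion is met, the medical monitor will review the unblinded allocation before Cohort 2 opens. Without that sentence the change brings a pause and an assessment but no required unblinded look. Section 11.8 and the criteria for Cohorts 2 to 4 can stay as they are.

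The cost is two lines of text, with no added subjects or procedures. Escalation already waits for Day 7 results, so the review can often fit in that interval.

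The downside is an occasional extra review, which the monitor can close by resuming, and unblinding the monitor to Cohort 1 when it happens. With no drug effect the chance is about 2% per event type at the assumed 9% rate, and higher over several event types together. At p = 50% with saline clear it is 25%. In Cohort 1 the Grade 2 count would equal the Grade 3 count of two, but the 11.7 Grade 2 criterion would still require relatedness, which its Grade 3 criterion does not. The change spares no exposure within Cohort 1.

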5 TREATMENT

5.1 Randomization and Blinding

The randomization schedule will be generated using SAS Version 9.4 or later (SAS Institute Inc, Cary, North Carolina), which will link sequential volunteer randomization numbers to treatment codes. The randomization schedule and the volunteer-specific emergency unblinding documentation will be provided to the unblinded pharmacist(s) at the clinic site.

Study participants and study team (PI and associate Investigators and study staff) will be blinded throughout the entire study. The study team will be unblinded after the Study Day 90 visit, all laboratory (and immunogenicity) results are available, and the final monitoring visits has occurred.

The infusion will be provided in an opaque bag to obscure the bag, since SAB-176 may develop bubbles similar to what is seen with IVIg, if the product is agitated. This process has been used in other studies (INSIGHT influenza IVIG) and was successful in maintaining blinding of the study team.

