- Other adverse reactions not specified, that are concerning for infusion related adverse events

After clinical assessment, and resolution or improvement of the event of concern, the infusion may be resumed. If the event is not resolving in a reasonable amount of time, the infusion will not be resumed.

However, in order to establish absolute criteria for stopping an infusion – the treatment should be immediately stopped should any of the following occur:

- Profound hypotension (systolic blood pressure < 85 mmHg)
- Shortness of breath, wheezing, or sustained (i.e., ≥ 10 seconds) oxygen saturation < 92% on room air
- Severe (Grade ≥ 3) local infusion site reactions, including pain, tenderness, erythema, or swelling as defined in the protocol-specified toxicity grading scale
- Body core temperature exceeding 38.5°C
- Suspected sepsis
- Severe chest pain
- Suspected anaphylaxis

The subject's actual time of drug administration will be recorded in the source documents.

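### The two-subject Grade 3 pausing trigger in Protocol 11.7 omits *or higher*, so read literally it does not cover a Grade 3 and 4 or a Grade 4 and 4 pair (minor)

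*Protocol*

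**What the plan says.** Section 11.7 of the Protocol lists seven triggers. Meeting any one of them closes the study to further enrollment until the sponsor medical monitor has assessed the case.

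- The third trigger fires when "Two or more subjects develop the same or clinically similar Grade 3 AE or laboratory abnormality". It has no causality condition.
- The second begins "Three or more subjects in the same cohort experiencing the same Grade 2 or higher adverse effect" and counts only events at least possibly attributed to study drug.
- The first is any serious adverse event at least possibly attributed to study drug.
- The fourth to sixth are renal.
- The seventh concerns clotting tests: "Grade 2 toxicity in PT and/or PTT (i.e. one grade 2 PT and one grade 2 PTT would meet this pausing rule". The words leading into it name serum creatinine.

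Section 11.8 sets the escalation rules. One is "Two or more subjects across all cohorts experience the same Grade 3 or higher adverse effect that can be possibly, probably, or definitively attributed" to study drug. Another, without a causality condition, is "Any immediate hypersensitivity or cytokine storm events". If a criterion is met, the study does not move to the next dose. In addition, "If any of the above criteria are met at any time, then the medical monitor will evaluate unblinded study data" and decides on continuation.

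Section 5.3 stops an individual infusion for "Severe (Grade ≥ 3) local infusion site reactions", among other criteria.

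**The concern.** A safety threshold normally covers the named grade and everything worse. This one names Grade 3 alone, directly below a bullet that does say *or higher*. The contrast invites a literal reading, under which two Grade 3 events hold the study and two worse events of the same kind do not.

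The bullet has a particular role. The first two triggers need attribution, the fourth to sixth are renal, and the seventh is PT/PTT. The third is therefore the only trigger that neither depends on a causality judgment nor is tied to one organ system. Section 10.2 records the principal investigator's judgment of causality, and 5.1 states: "Study participants and study team (PI and associate Investigators and study staff) will be blinded throughout the entire study".

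What is at stake is the automatic hold while a case is assessed. After the first three subjects of a cohort and the committee's review, 3.2 allows up to three subjects to be dosed per day. The Table 2 example doses subjects 4 to 10, seven people, on three consecutive days. A debate over whether Grade 4 counts could overlap with further dosing.

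**Working it through.** The protocol states no operating characteristic for the pausing rules, so there is no figure to reproduce. The check is a comparison of texts.

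**Step 1. Grade-based rules.**

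| Place | Subject of the rule | Lowest grade | Extends upward? |
|---|---|---|---|
| 5.3 | Infusion-site reaction | 3 | Yes |
| 11.7, bullet 2 | Three related cases in one cohort | 2 | Yes |
| 11.7, bullet 3 | Two subjects, any attribution | 3 | **No** |
| 11.7, bullet 4 | Creatinine | 2 | Yes |
| 11.7, bullet 7 | PT/PTT | 2 | Yes |
| 11.8, bullet 5 | Two related cases across cohorts | 3 | Yes |
| 11.8, bullet 6 | Three of the first 10 subjects, later 30%, related | 2 | Yes |
| 11.8, bullet 7 | Creatinine | 2 | Yes |

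That is 1 + 4 + 3 = 8 rules, of which 8 − 1 = 7 extend upward.

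**Step 2. Pairs.** Section 10.1 cites the DAIDS table but does not reproduce it. I assume that Grade 4 is the only non-fatal grade above 3, and leave death to 4.8. The possible pairs are then 3+3, 3+4 and 4+4. Literally, only 3+3 meets bullet 3.

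**Step 3. Other 11.7 triggers.** A 3+4 or 4+4 pair still pauses the study in any of these cases:

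- Either event is serious and at least possibly related (bullet 1). Section 10.3 counts life-threatening and medically important events as serious, so this cover is wide. It is not complete, because 10.3 defines seriousness by outcome and medical judgment, and a laboratory grade alone does not make a value serious.
- A third related case of Grade 2 or higher occurs in the same cohort (bullet 2).
- The values meet a renal trigger (bullets 4 to 6) or the PT/PTT trigger (bullet 7).

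**Step 4. What 11.8 adds for the remaining pairs.**

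- *Both events related.* The Grade 3 or higher rule applies if the events are the same. Escalation is barred, and the medical monitor reviews unblinded data at any time. An 11.7 pause leads to the same monitor, so what is lost is the enrollment hold in the meantime.
- *Both judged unrelated.* The Grade 3 or higher rule does not apply. What remains is discretionary or case-specific: termination for a potential health hazard (4.8), interruption by the investigator (11.2.1), safety committee review (3.2, 11.4), and the hypersensitivity and cytokine-storm rule in 11.8.

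**Step 5. PT/PTT bullet.** The words naming serum creatinine repeat the opening of bullet 4, and a creatinine toxicity cannot occur in a clotting test. The example in parentheses mentions only PT and PTT, so the intended meaning is clear.

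**The case against.** The best reply is that nobody would apply the bullet literally. A safety committee would have to hold the study for two Grade 3 events and let it run after two worse ones. Every parallel rule extends upward, which points to a drafting omission. The list is also loose with grades elsewhere: bullet 7 covers Grade 2 and above, yet its example says only grade 2.

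The surrounding protection is also substantial. One serious event that is even possibly related pauses the study. Under 10.1.1, *possibly related* asks only for a reasonable temporal relationship and little evidence of a likelier cause. Two same-type events at these grades, with neither judged even possibly related, would be unusual in 27 healthy volunteers. Sections 4.8 and 11.2.1 and the committee need no attribution to act.

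Most of this stands, and it sets the size of the point. It does not make the text correct. The operative sentence stops at Grade 3, and the other safeguards either need attribution, are discretionary, or cover particular events.

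A reader might infer that Grade 4 events go unmonitored, or that 11.8 offers no more than a review. The documents do not support either. Section 11.8 bars escalation as well as calling for unblinded review, and the first 11.7 trigger already catches related serious events of any grade.

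**Conclusion.** The point holds as a minor wording fault in an operative safety rule. One of eight grade-based rules is not open upward, and it is the only general trigger that does not rest on attribution. The literal gap is confined to 3+4 and 4+4 pairs that meet no other 11.7 trigger. For related pairs of the same event, the loss is the automatic enrollment hold. For unrelated pairs, the 11.8 Grade 3 or higher rule does not apply either.

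This rests on reading the bullet as written and on taking Grade 4 as the only non-fatal grade above 3. Grade 4 was probably intended. The count of rules describes coverage, not likelihood. The protocol gives no Grade 3 or Grade 4 rate, so I attach no probability, and I assume such pairs are rare in this population.

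A reader might also infer from bullet 7 that the study lacks a working clotting trigger, which would matter because 8.1.1 relies on serial PT/PTT. The documents do not support that: the parenthetical settles the meaning, and the slip has no demonstrated operational effect.

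**What to change.** In the third bullet of 11.7, insert *or higher* directly after *Grade 3* and leave the rest unchanged. This matches the wording of the bullet above it and of the Grade 3 rule in 11.8.

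As an editorial correction in the same section, delete *a serum creatinine* from the PT/PTT bullet and keep its parenthetical.

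Both are wording edits that add no data, visits or subjects. The only downside of the first is a possible extra pause after a 3+4 or 4+4 pair, which would last until the sponsor medical monitor has assessed it. The second has no downside.
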